1. STUDY PROTOCOL

1.1 Objectives

The research aims to determine the differences in:

- Decrease in IL-1 β levels between benign paroxysmal positional vertigo (BPPV) patients receiving oral lumbrokinase DLBS1033 therapy and those receiving betahistine therapy.
- Decrease in TNF- α levels between BPPV patients receiving oral lumbrokinase DLBS1033 therapy and those receiving betahistine therapy.
- Decrease in VCAM-1 levels between BPPV patients receiving oral lumbrokinase DLBS1033 therapy and those receiving betahistine therapy.
- Quality of life between BPPV patients receiving oral lumbrokinase DLBS1033 therapy and those receiving betahistine therapy.
- Time to improvement of dizziness symptoms between BPPV patients receiving oral lumbrokinase DLBS1033 therapy and those receiving betahistine therapy.

1.2 Design and Methods

- Type of research: This study is a clinical trial with a double-blind randomized controlled trial design.
- Place and time of research: The study was conducted at the neurology polyclinic of [name] General Hospital, Surakarta. Data collection began after obtaining ethics committee approval and continued until the required sample size was met, from April to August 2024.
- Research population: The actual research population consists of patients at the neurology polyclinic of [name] General Hospital, Surakarta, who met the inclusion and exclusion criteria.
- Research subjects: Subject selection was carried out using purposive sampling.
 - Inclusion criteria: BPPV patients at the neurology polyclinic of [name] General Hospital, aged 18-65 years, diagnosed by a neurologist or neurology polyclinic resident based on a history of worsening vertigo, nausea, vomiting, and imbalance with head movements, and findings of torsional nystagmus with latency, fatigability, and duration less than 60 seconds on Dix-

Hallpike maneuver; able to speak, read, and write Indonesian; and willing to cooperate as research subjects by signing the informed consent form.

- Exclusion criteria: Pregnant and breastfeeding patients; patients with neurological deficits indicative of central vertigo based on anamnesis and physical examination; patients with a history of ear infection, hearing impairment, tinnitus, and head trauma; patients with thyroid disorders, diabetes mellitus, genu osteoarthritis, history of neoplasm, history of heart disease and hypertension, history of ear/mastoid surgery, and currently experiencing other inflammatory and infectious conditions; patients with cognitive impairment based on attention and memory examination; patients participating in other clinical studies within 30 days before screening.
- Drop-out criteria: Patients who could not complete the entire research procedure; patients who did not follow procedures properly; patients who did not complete the DHI and VSS-SF questionnaires after receiving therapy.
- Sample size: The minimum sample size was calculated using Sopiyudin's sample size¹ formula with a 95% confidence interval (CI) and 5% confidence limits. Based on a total population of 751 peripheral vertigo patients treated at the neurology polyclinic of [name] in the last year, the calculation resulted in a minimum sample of 40 patients. An additional 10% was added to anticipate dropouts, making the total sample size 44 patients.
- Variable identification:
 - Independent variable: BPPV therapy.
 - Dependent variables: inflammation level, quality of life, time to improvement of dizziness symptoms in BPPV patients.
 - Confounding variables: age, body mass index, gender.
- Operational definition of research variables:
 - BPPV therapy: Administration of oral lumbrokinase (DLBS 1033, 2x490 mg daily) or betahistine (2x12 mg daily) for 14 days to diagnosed BPPV patients.
- Research instruments: Dizziness Handicap Inventory (DHI) and Vertigo Symptom Scale Short Form (VSS-SF) questionnaires, and biomarker examination (IL-1 β , TNF- α , VCAM-1) using Human Quantikine R&D Systems kits on a Thermo Fisher Invitrogen auto-analyzer according to manufacturer specifications.
- Randomization protocol: The study protocol involved a two-block randomization to ensure balanced group assignments. The random sequences for the group allocation were generated by independent personnel of the direct study management and kept in sealed

envelopes. This allocation concealment ensured that neither the investigator team nor the participants knew their assigned treatment. Each package was coded with the subject identification number according to the generated random number and assigned to each eligible subject. These codes remained unrevealed until the study's completion.

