2.2 Specific Statistical Methods

- Normality test: The Kolmogorov-Smirnov test was used to check the normality of the data distribution for all variables. The Kolmogorov-Smirnov test was performed to verify the assumption of normal distribution for all variables, confirming that the data met this critical assumption for the subsequent parametric tests.
- Comparison between groups (day 7 and day 14):
 - Independent T-test: This test was used to determine significant differences between the oral lumbrokinase DLBS1033 group and the betahistine group for:
 - Mean DHI scores,
 - Mean VSS-SF scores,
 - Mean TNF- α levels,
 - Mean IL-1 β levels,
 - Mean VCAM-1 levels.
- Analysis of symptom improvement time (multiple repeated ANOVA):
 - Given the significant statistical differences found with the independent T-test, further analysis regarding the time to symptom improvement in BPPV patients receiving oral lumbrokinase DLBS1033 was performed using multiple repeated ANOVA.
- Post-hoc analysis: Tukey B post-hoc test was used to compare the mean scores/levels between groups.

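### Drop-out criteria apply after randomisation and no analysis set is named, so the day-7 and day-14 comparisons are probably of completers only

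*Combined protocol and SAP*

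**What the plan says.** Three drop-out criteria appear in section 1.2. The first two cover "Patients who could not complete the entire research procedure; patients who did not follow procedures properly". The third covers "patients who did not complete the DHI and VSS-SF questionnaires after receiving therapy". Each is a status of the patient, not of a single outcome or visit. The word *properly* has no threshold and no named assessor.

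The sample-size paragraph of the same section starts from a minimum of 40 and continues: "An additional 10% was added to anticipate dropouts, making the total sample size 44 patients". Data collection "continued until the required sample size was met, from April to August 2024"; the text does not say whether a drop-out counts towards that size.

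On blinding, the randomisation paragraph says of the allocation codes: "These codes remained unrevealed until the study's completion".

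Sections 2.1 and 2.2 are the whole SAP. They specify the software, a normality test, independent t-tests at day 7 and day 14 to "determine significant differences between the oral lumbrokinase DLBS1033 group and the betahistine group" on DHI, VSS-SF and the three biomarkers, a repeated-measures ANOVA and a post-hoc test. They name no analysis set and do not say what happens to a patient who meets a drop-out criterion.

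**The concern.** Randomisation makes the two arms comparable at the time of allocation. A rule that removes patients for what happens later (stopping, not adhering, not returning a questionnaire) can undo this if the reasons differ between arms and are linked to outcome. Poor tolerability or lack of response under one treatment would be examples.

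There is a second, more mechanical loss. Because the criteria attach to the patient, someone who gave blood but did not complete the DHI and VSS-SF could lose usable IL-1β, TNF-α and VCAM-1 values. Someone who attended day 7 but missed day 14 could lose the day-7 values. Three of the five objectives in section 1.1 concern those biomarkers.

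With about 40 patients, a handful of exclusions is a material fraction of each arm. Even without bias, two analysts following this text could analyse different sets of patients.

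**Working it through.** **1. The plan's own figure.** 40 × (1 + 0.10) = 44, which reproduces the stated total. Losing the 4 extra patients returns 44 − 4 = 40. The trial is therefore sized to have 40 left after drop-outs, which fits a completer analysis but does not prove one.

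**2. The passages side by side.** The drop-out criteria say who is a drop-out. The sample-size paragraph allows for drop-outs as expected losses. The SAP compares the two groups without saying who is in them. Nothing keeps a drop-out in the analysis and nothing explicitly removes one. Taken together, the first two point to removal.

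**3. What removal could do.** The documents give no losses by arm, no SD and no link between drop-out and outcome, so the inputs here are assumptions: 22 per arm (44 split evenly), normal outcome with SD 1, no true difference, 4 losses in all, two-sided t-test at 0.05. Each patient has a drop-out score with correlation ρ to the outcome, and the worst-scoring patients leave. Bias is the expected difference in means between those who remain. Results are from 100,000 simulated trials per cell for the first two patterns and the last; the equal-loss row is a separate run of the same model.

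| Who leaves | ρ = 0.3 | ρ = 0.5 | ρ = 1 (extreme) |
|---|---|---|---|
| 4 from one arm, 0 from the other | 0.09 SD, 6.1% | 0.15 SD, 8.1% | 0.31 SD, 19.2% |
| 3 from one arm, 1 from the other | 0.04 SD, 5.5% | 0.07 SD, 6.2% | 0.15 SD, 10.7% |
| Worst 2 from each arm | – | 0 SD, 5.6% | 0 SD, 7.7% |
| Worst 4 of all 44, regardless of arm | 0 SD, about 5% | 0 SD, about 5% | 0 SD, about 5% |

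Each cell gives bias and type I error. At ρ = 0 the first two patterns give no bias and 5.0%. The bias favours the arm that lost its worst patients.

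Two things follow. With no true difference, bias needs loss that depends on both arm and outcome. The type I error, however, can rise a little without any bias: forcing the worst patients out of each arm in equal numbers trims both tails of the comparison and gives 5.6% at ρ = 0.5. Much of the 6.2% in the 3-against-1 row at that correlation is this trimming, not imbalance.

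**4. If there is a true difference.** With the worst 4 of 44 leaving regardless of arm, a true difference of 0.5 SD shrinks by 0.012 and 0.032 SD at ρ = 0.3 and 0.5. A true difference of 0.8 SD shrinks by 0.018 and 0.051 SD.

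**5. What keeping collected values achieves.** If 4 patients in one arm miss the questionnaires and their biomarker values are discarded, the biomarker bias is 0.09 SD (ρ = 0.3) to 0.15 SD (ρ = 0.5). If those values are kept, it is 0. In the extreme case where the four worst at day 7 in one arm miss day 14, keeping their day-7 values takes the day-7 bias from 0.31 SD to 0. The day-14 bias is not removed: it is 0.12, 0.19 or 0.25 SD at an assumed day-7/day-14 correlation of 0.4, 0.6 or 0.8.

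**6. Cost of including non-adherent patients.** If 2 of 22 in one arm get no benefit, an assumed effect of 0.80 SD is seen as 0.80 × 20/22 = 0.73 SD. Simulated power is 64%, against 71% when those two are left out and their leaving is unrelated to outcome.

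**The case against.** The strongest objection is that exclusion is inferred. A recruitment allowance of 10% looks the same whether drop-outs are removed or every available value is used, and the SAP could be carried out either way. This stands, and it is why the point is put as a likely reading. A reader might infer that the documents state that drop-outs were excluded; they do not.

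Second, the sizes rest on assumed loss patterns. If arm plays no part in who leaves, a 4:0 split in either direction has a chance of about 11% and an even 2:2 split is the most likely (39%). This also stands. A reader might take the 0.31 SD and 19% cells as the expected harm. They require the four worst outcomes all to leave one arm, and nothing in the documents suggests that.

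Third, the trial is double-blind with closed codes, treatment lasts 14 days and planned loss is about 4 of 44. A reader might infer that *properly* could be applied selectively against one arm. The closed codes make that unlikely, and the documents give no sign of it. Blinding does not, however, prevent attrition driven by tolerability or lack of response, which needs no knowledge of allocation.

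Finally, the work is described as done: the SAP refers to "Given the significant statistical differences found with the independent T-test". Advice cannot be fully prospective, but the set analysed can still be declared and, where data exist, the comparison rerun.

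**Conclusion.** The point holds as a matter that should be fixed, with medium confidence. The plan has a patient-level, post-randomisation drop-out rule and no analysis set, and the likely reading is that the between-arm t-tests at day 7 and day 14 are of completers. On that reading, values already collected can be discarded.

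The size and direction of any bias are unknown, and it may be nil. Under the stated assumptions, with all four losses in one arm and a correlation of 0.3 to 0.5, it is 0.09 to 0.15 SD with type I error of 6–8%; with losses of 3 against 1 it is about half that. These are illustrations, not estimates for this trial. The documents do not support a claim that the reported differences are biased, nor the opposite claim that loss unrelated to arm always leaves the type I error at 5%.

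**What to change.** State in the protocol and SAP:

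- Meeting a drop-out criterion, including non-adherence, does not remove a patient from the analysis.
- The main comparison at each visit includes every randomised patient, in the allocated arm, with a value for that outcome at that visit. A missing questionnaire then leaves the biomarkers in, and a missed day 14 leaves day 7 in.
- The completer set is a sensitivity analysis only, with *properly* defined for it without reference to arm or outcome.
- Drop-outs and their reasons are reported by arm, including patients with no post-therapy value.

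Because collection and analysis are described in the past tense, apply this as a re-analysis where drop-outs' data were kept (the documents do not say whether they were), and label it post hoc if the codes are open.

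The cost is wording plus a rerun of the same t-tests. The downside is slight dilution by non-adherent patients, as in the 0.80 to 0.73 SD example. Patients with no post-therapy value are not recovered, so some bias may remain. A mixed model over both days is one option for handling missing values, but it is not part of this correction.

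### The sample size of 40 is justified by single-estimate precision inputs that do not size the two-arm comparison, and 40 cannot be reproduced from them

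*Combined protocol and SAP*

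**What the plan says.** The Sample size item in section 1.2 names a formula by its cited source and applies it "with a 95% confidence interval (CI) and 5% confidence limits". It continues "Based on a total population of 751 peripheral vertigo patients" seen at the clinic in the previous year, and reports that "the calculation resulted in a minimum sample of 40 patients". Ten per cent is then added for dropouts, "making the total sample size 44 patients". The equation is not written out. No expected proportion, SD, between-group difference or power appears.

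Elsewhere the document describes a comparative trial. Section 1.1 opens with "The research aims to determine the differences in" and lists outcomes contrasted between lumbrokinase and betahistine. Section 1.2 calls the study a "double-blind randomized controlled trial design" and uses "two-block randomization to ensure balanced group assignments". SAP section 2.2 compares the two groups' means on DHI, VSS-SF, TNF-α, IL-1β and VCAM-1 by independent t-test at days 7 and 14. The SAP has no sample-size text of its own.

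Section 1.2 also says that data collection "continued until the required sample size was met", so this figure determined when recruitment ended.

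**The concern.** A confidence level, a limit of precision and a finite source population are what one needs to estimate a single quantity in a single population. A two-group comparison of means is sized from a difference, an SD, a significance level and a power. Three of these four are absent, and the fourth appears only if the 5% is read as a significance level. A two-means calculation would also have no use for the population of 751.

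The justification therefore looks as if it answers a different question from the one the trial asks. The 95% and 5% wording also suggests tight precision, which 20 or so patients per group cannot give for a between-group difference. Without a stated sensitivity, a reader cannot tell which differences the trial could detect, or how to read any outcome that is not significant.

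**Working it through.** **Inputs from section 1.2:** 95% confidence (z = 1.96), 5% limits (scale not stated), N = 751, result 40, 10% added.

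**Dropout step.** 40 × 1.10 = 44. This follows from 40.

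**Attempt to reproduce 40.** The equation is not shown, so each reading below is an assumption.

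*Single proportion, absolute limits d = 0.05, finite population correction:* n0 = 1.96² p(1 − p)/d², then n = n0/(1 + (n0 − 1)/751).

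| Assumed p | n0 | n after correction |
|---|---|---|
| 0.5 | 384.1 | 254.4 |
| 0.1 | 138.3 | 116.9 |
| 0.05 | 73.0 | 66.6 |
| 0.028 (or 0.972) | about 42 | about 40 |

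At p = 0.5, a corrected n of 40 corresponds to d = 0.151, that is, limits of about 15 points and not 5.

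*Population and limit only:* N/(1 + N e²) with e = 0.05 gives 751/(1 + 751 × 0.0025) = 751/2.8775 = 261.

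*Other readings that can reach 40, each with an unstated input:*
- Single proportion without the correction: p of about 0.027 or 0.973.
- Limits of 5% relative to p, with the correction: p of about 0.973.
- Single mean with limits of 5% of the mean, with the correction: coefficient of variation of about 0.166.

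No reading that uses only the stated inputs, or the conventional p = 0.5, comes near 40.

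**What 40 or 44 gives the actual comparison.** Assumptions: equal groups, one two-sided 5% two-sample t-test, no multiplicity adjustment. Power is from the noncentral t distribution. The 95% CI half-width is t(0.975, 2n − 2) × √(2/n), in SD units.

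| | 20 per group (40) | 22 per group (44) |
|---|---|---|
| Difference with 80% power | 0.91 SD | 0.86 SD |
| Power at 0.5 SD | 34% | 37% |
| Power at 0.8 SD | 69% | 74% |
| 95% CI half-width | 2.024 × 0.316 = 0.64 SD | 2.018 × 0.302 = 0.61 SD |

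The 0.5 and 0.8 SD values are illustrative; the documents give no target effect.

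**The case against.** The best defence is that the cited source may contain a two-means equation and that the 5% is loose wording for a significance level. With 80% power and a difference of 0.9 SD, the normal approximation gives 2 × (1.96 + 0.84)²/0.9² = 19.4, so 20 per group and 40 in total. This is possible, and it is one reason not to call 40 an arithmetic error. It does not rescue the text: the difference, SD and power would still be unstated, and the 751 would have no role.

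It can also be said that nothing shows 40 was too few, that SAP section 2.2 reports some significant t-tests, and that observed confidence intervals tell a reader more than retrospective power. The first two are true. They limit the interpretive harm to outcomes that were not significant, but leave the justification as it is. On the third, observed intervals should indeed be reported. The sensitivity proposed here depends only on the numbers analysed and not on observed effects, so it complements them. It covers one test, not the full set of five outcomes at two time points, and should say so.

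Finally, neither the validity of the randomized comparison nor the type I error of any test depends on how 40 was justified. That is correct, and it is why the remedy is confined to wording.

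**Conclusion.** The concern holds on both counts. As written, the basis for 40 consists of inputs for the precision of one estimate and does not size the between-group comparison of means. Separately, 40 does not follow from the stated inputs: the assumed single-proportion formula with correction gives about 254 at p = 0.5, and reaching 40 needs an unstated value such as p of about 0.028 or 0.972.

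Two limits apply. The equation is not visible, so a miscalculation is not established. The finding also does not show that the trial was too small, only that the document gives no means of judging. Under equal groups and a single unadjusted test, the design had 80% power for differences of about 0.9 SD and roughly one chance in three of detecting 0.5 SD. Because this figure set the end of recruitment and is the only justification of size, it must be corrected.

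**What to change.** Stop presenting the 95%, 5% and 751 calculation as the justification for the group comparison. Then:

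1. If a two-arm calculation was made, replace the text with its endpoint, difference, SD and power.
2. If not, state: *The number 40 (44 with 10% added) was not derived for the comparison between the two treatment groups.*
3. Keep the 5% precision wording only if the formula and the expected proportion or SD actually used are given and reproduce 40. Otherwise remove it.

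In either case add, labelled as retrospective and completed with the numbers actually analysed: *With [n1] and [n2] patients analysed, one unadjusted two-sided 5% two-sample t-test has 80% power for a difference of [x] SD; the 95% CI half-width is [y] SD. Non-significant results are not evidence of no difference.* For 20 per group, x = 0.91 and y = 0.64; for 22 per group, x = 0.86 and y = 0.61. Recompute for any other numbers.

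The cost is one paragraph. Enrolment, data and analyses do not change. The drawback is that the stated justification becomes less favourable than the present wording suggests.

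### Age, BMI and gender are named as confounders, but neither the randomisation nor any between-arm analysis uses them; add a covariate-adjusted model beside the t-tests

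*Combined protocol and SAP*

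**What the plan says.** Under variable identification, protocol section 1.2 lists "Confounding variables: age, body mass index, gender". It gives no strength of association, no source and no statement of how the three variables will be used.

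The same section describes the allocation: "The study protocol involved a two-block randomization to ensure balanced group assignments". No stratification factor or minimisation is mentioned. The total is 44 patients, a minimum of 40 plus 10% for dropout.

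SAP section 2.2 contains the whole analysis:
- a Kolmogorov-Smirnov check of normality;
- t-tests at day 7 and day 14 on DHI, VSS-SF, TNF-α, IL-1β and VCAM-1 ("Independent T-test: This test was used to determine significant differences between the oral lumbrokinase DLBS1033 group and the betahistine group for" those means);
- a repeated ANOVA on symptom improvement time, described for the lumbrokinase patients;
- Tukey B comparisons of means.

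Age, BMI and gender do not appear anywhere in the SAP.

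**The concern.** The protocol gives three variables a label that implies a link with the outcomes, and the SAP then says nothing about them. A two-sample t-test cannot take covariates, and none is named for the other procedures. Balancing the number of patients per arm does not balance age, BMI or gender.

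Two things are at stake. First, in a trial this small a chance imbalance in a prognostic variable passes straight into the estimated arm difference, and the plan has no pre-specified way to respond when the baseline table shows one. Any adjustment would then be chosen after the data are seen. Second, the outcome variance that these variables explain, if any, widens every confidence interval.

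**Working it through.** **Inputs.** From section 1.2: "the calculation resulted in a minimum sample of 40 patients", then "An additional 10% was added to anticipate dropouts", "making the total sample size 44 patients". Two arms with balanced numbers imply 44/2 = 22 per arm, or 40/2 = 20 after the allowed dropout. The 1:1 ratio is inferred. The documents give no effect size, SD, power, covariate correlation or R-squared, so those below are assumptions shown as ranges.

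**The plan's own figure.** 40 × 1.10 = 44 reproduces. The 40 does not follow from what is stated. With a population of 751, 95% confidence and 5% limits, the finite-population formula for a proportion at p = 0.5 gives 751 × 0.25 × 1.96² / (0.05² × 750 + 1.96² × 0.25) = 254.4, or 255. A result of 40 needs p of about 0.028, or limits near 15% at p = 0.5. That is a separate matter, and this point uses only the resulting 44.

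**Chance imbalance.** The standardised arm difference in a continuous covariate has SD √(2/n) with n per arm.

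| | 22 per arm | 20 per arm |
|---|---|---|
| SD of chance difference | √(2/22) = 0.30 | √(2/20) = 0.32 |
| P(difference beyond 0.5 SD), one covariate | 9.7% | 11.4% |
| At least one of three | 1 − (1 − 0.097)³ = 26% | 1 − (1 − 0.114)³ = 30% |

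The last row treats the three as independent and approximately normal, which is rough for gender. By the hypergeometric distribution, with 50% to 65% women assumed, the gender split differs by at least 20 percentage points in 13% to 20% of randomisations at 22 per arm.

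**Effect on the estimate.** Shift = correlation × imbalance. A 0.5 SD imbalance with an outcome correlation of 0.1, 0.3 or 0.5 moves the arm difference by 0.05, 0.15 or 0.25 outcome SD. The unadjusted standard error is 0.30 SD, so 0.15 SD is half of one standard error.

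**Type I error of the unadjusted t-test.** In simulation (40,000 null trials per setting, blocks of two) it stays between 4.9% and 5.1% for a joint R-squared of 0.10 to 0.30. Restricted to null trials with an imbalance beyond 0.5 SD in one covariate correlated 0.3 with the outcome, it is about 8%.

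**Power with and without adjustment.** At 22 per arm the t-test has 80% power at 0.865 SD. This is a reference value and not a planned effect. Adjusting for three covariates multiplies the variance by (1 − R²) × (1 + 3/(44 − 6)) = (1 − R²) × 1.079 and reduces the residual degrees of freedom from 42 to 39.

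| Joint R² (assumed) | Variance ratio | Adjusted power |
|---|---|---|
| 0 | 1.08 | 77% |
| 0.10 | 0.97 | 81% |
| 0.20 | 0.86 | 85% |
| 0.30 | 0.76 | 90% |

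Break-even on variance: R² = 1 − 1/1.079 = 0.07 (0.08 at 20 per arm).

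**The case against.** The strongest reply is that randomisation already deals with confounding. That stands as far as bias goes. A reader might infer from the word confounding that the arm comparison will be systematically distorted. The design does not support this: allocation is random and concealed, and the t-test's error rate holds over randomisations. Its confidence interval already allows for chance imbalance on average.

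It can also be said that the plan never promises to adjust. That is correct. A reader might take the list to mean that the protocol requires these variables in the analysis, but section 1.2 only names them. The inconsistency is a list with no stated use.

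Nor do the documents show that adjustment would gain power. No R-squared is given. The exclusion of diabetes, hypertension, heart disease, thyroid disorders and current inflammatory conditions may weaken the link between these variables and the biomarkers. Limiting age to 18-65 neither balances age nor adjusts for it.

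Finally, section 2.2 is written in the past tense and refers to significant t-test differences already found. Replacing the main analysis now would be a post hoc change. This limits the remedy to adding a model. It does not remove the omission.

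**Conclusion.** The omission is real: three named confounders have no role in either the randomisation or the analysis. It is a weakness in precision and conditional accuracy, and the planned tests remain valid without adjustment.

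At about 22 per arm, a given continuous covariate is out of balance by more than 0.5 SD in about 10% of randomisations. Power at the reference effect would move from 80% to between 77% and 90% as the joint R-squared runs from 0 to 0.30. Because the documents do not place R-squared above or below 0.07, the direction of the power change is unknown. The size rests on the inferred 1:1 ratio and on assumed correlations. The case for a pre-specified adjusted model therefore rests mainly on giving the listed variables a defined use, and on having an answer ready if the arms turn out to differ on them.

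**What to change.** In SAP section 2.2, add for each of the five outcomes, at day 7 and at day 14, a linear model (ANCOVA) with arm, age and BMI as continuous terms, gender, and the pre-treatment value of that outcome where it was measured. The baseline value belongs in the model because the biomarker objectives in section 1.1 are framed as decreases. Report the adjusted mean difference with its 95% CI beside the unadjusted t-test. Fix the covariates by name, and do not select them by baseline significance tests.

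If t-test results are already known, label the adjusted model as added later and do not let it silently replace the t-test. If the variables are not to be used, say why they are listed.

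Cost: three degrees of freedom for age, BMI and gender (42 to 39 with all 44 patients), one more with the baseline value, and about 3 points of power if the three explain nothing. The change is to SAP text and analysis only, provided the data exist. The sponsor should confirm that BMI was recorded, since section 1.2 defines only the therapy operationally and the procedures in section 1.4 do not name BMI.

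### The block size behind the two-block randomisation is undefined; if it is two, recognising the first patient of a pair before the partner enrols discloses the partner's arm

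*Combined protocol and SAP*

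**What the plan says.** Section 1.2 (Randomization protocol) gives one sentence on the scheme: "The study protocol involved a two-block randomization to ensure balanced group assignments". It states no block size, no number of blocks, no variation in size, and nothing on who knew the scheme.

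The same item lists safeguards. The sequence came from people independent of the study management and was held in closed envelopes. Packages carried subject numbers, and the codes stayed closed to the end. Section 1.2 also calls the trial double-blind.

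The two treatments are different products: "Administration of oral lumbrokinase (DLBS 1033, 2x490 mg daily) or betahistine (2x12 mg daily) for 14 days to diagnosed BPPV patients". No section describes matching appearance, over-encapsulation or a double-dummy.

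On recruitment at the single clinic, section 1.2 says "Subject selection was carried out using purposive sampling", followed by inclusion and exclusion criteria. On numbers, it says "the calculation resulted in a minimum sample of 40 patients", then "An additional 10% was added to anticipate dropouts", "making the total sample size 44 patients".

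SAP section 2.2 compares mean DHI, VSS-SF, TNF-α, IL-1β and VCAM-1 between arms at days 7 and 14 by independent t-test, with no baseline term.

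**The concern.** In a two-arm trial, two-block can naturally be read as blocks of two. That is the most predictable form of permuted block, because the only possible blocks are AB and BA. Closed envelopes and coded packages protect the list. They do not protect against deduction once a treatment has been recognised, and the documents leave open how recognition was prevented.

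If a recruiter could deduce the next arm, the choice of whom to enrol next could depend on it. The resulting baseline imbalance would pass straight into the day 7 and day 14 t-tests, which have no baseline adjustment to absorb it.

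**Working it through.** **Inputs.** From section 1.2: two arms and 44 allocations. Assumed: 1:1 allocation, inferred from "to ensure balanced group assignments"; and block size, which the documents do not give, so 2, 4, 6 and 22 are all shown. The figure of 44 reproduces as 40 × 1.10 = 44. The documents give no figure for predictability.

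**Step 1. Allocations certain to someone who knows all earlier assignments and the block boundaries.** For block size 2m the expected certain share is 1/(m+1).

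**Step 2. Best-guess success.** The guess is always the arm with fewer patients so far, with full knowledge of past assignments. The expected rate is [m + (4^m / C(2m,m) − 1)/2] / 2m. For m = 1 this is [1 + (4/2 − 1)/2]/2 = 0.75. For m = 2 it is [2 + (16/6 − 1)/2]/4 = 0.708.

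**Step 3. One recognised patient only.** The chance that the next patient in the same block gets the other arm is m/(2m − 1).

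| Block size | Certain share (of 44) | Best-guess rate | Next is the other arm, one patient recognised |
|---|---|---|---|
| 2 | 50% (22) | 75.0% | 1/1 = 100% |
| 4 | 33% (14.7) | 70.8% | 2/3 = 67% |
| 6 | 25% (11) | 68.3% | 3/5 = 60% |
| 22 (two blocks) | 8% (3.7) | 61.2% | 11/21 = 52% |

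For a random mix of sizes 4 and 6, simulation of sequences of 44 gives a best-guess rate of about 69%.

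**Step 4. Which patients disclose what.** With blocks of two, a recognised patient discloses the next assignment only if first in a pair (22 of 44 positions). A second member discloses the partner already enrolled, and the next allocation stays 50:50. Of the 43 consecutive pairs of patients, 22 lie within a block.

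**Step 5. Which baseline check would detect steering.** Suppose second members are chosen 0.5 SD higher when the coming arm is A and 0.5 SD lower when it is B.
- All first against all second members: (0.5 − 0.5)/2 = 0 SD, so the check sees nothing.
- A against B overall, with half of each arm affected: 0.25 − (−0.25) = 0.50 SD.
- A against B among second members: 0.5 − (−0.5) = 1.00 SD.

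Only the last contrast isolates the effect. With about 11 second members per arm, its standard error is √(1/11 + 1/11) = 0.43 SD.

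**The case against.** The strongest reply is that blocks of two is one reading of an undefined term. With two blocks of 22, a recognised patient moves the odds only from 50% to 52%. This stands, and the conclusion has to be conditional.

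Second, the 75% and 50% figures assume an observer who knows the relevant earlier assignments. The plan describes double-blinding, independent generation and closed codes, and nothing says recruiters knew the block size. This also stands as a limit on likelihood. It does not remove the exposure, because the means of masking two different products are not described. It is fair to add that the masking gap is a defect in its own right, and that changing the block size does not cure it.

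Third, recognition must come before the partner enrols. If enrolment filled April to August (153 days), 153/44 is about 3.5 days between patients. Recognition first made at the day 7 visit would usually be too late, so mainly recognition at or soon after dispensing matters.

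Fourth, a reader might infer from the mention of purposive sampling that recruiters were free to pass over eligible patients. The documents do not say so; explicit eligibility criteria follow the term.

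**Conclusion.** The concern holds in conditional form. The plan leaves the block size undefined. If it was two, half of the allocations (22 of 44) were determined by the one before, and one early recognition of a first-of-pair patient disclosed the partner's arm with certainty. If two blocks of 22 were used, the problem is small.

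Two stronger readings are tempting and not supported. One is that any unmasked patient reveals the next assignment; even with blocks of two, that is true only of first members. The other is that randomisation was undone and the comparisons are biased. That would need recognition, deduction and selective enrolment together, and the documents show none of these. The finding is a weakness that is cheap to close or to check. It rests on 1:1 allocation and on the block-of-two reading.

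**What to change.** **For a list not yet used.** Specify 1:1 permuted blocks of randomly varied size (4 and 6), generated by the independent person, with sizes not disclosed to recruiting staff. The best-guess rate falls only from 75% to about 69%. The main gain is that one recognised patient no longer gives certainty. The cost is a new list and one sentence; final arm sizes may differ by up to three if the last block is incomplete.

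**If allocation is already complete,** as the past tense and the April to August 2024 dates suggest, do not rewrite the sentence, since that would misreport what was done. Instead:

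- Report the block size actually used, whether it varied, who knew it, and how the two products were made indistinguishable.
- Replace the unadjusted t-tests at days 7 and 14 with comparisons adjusted for the baseline value of each outcome (for example ANCOVA), labelled as a change to the analysis. This assumes that baseline values exist. The objectives imply them for the biomarkers by speaking of decreases; for DHI and VSS-SF this must be confirmed. Adjustment removes only imbalance in what was measured.
- If blocks of two were used, compare baseline values between arms among second members of pairs, using all randomised patients. Do not compare first with second members, where opposite shifts can cancel. With about 11 per arm, a null result is weak reassurance.
- If two blocks of 22 were used, say so.

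The cost is a few sentences of reporting and a re-analysis of existing data.
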